# Statistical Analysis Plan

## SYLVI- study

### Power Calculation

The power calculation is based on our previous study showing that the Matsuda index decreases 23% (from 7.3 [ $\pm 2.9$ ] to 5.6 [ $\pm 2.8$ ]) during the use of COC containing EE for nine weeks 1. COCs containing EV have not been shown to affect glucose tolerance 2–4. Therefore we hypothesize that the Matsuda index decreases significantly in the EE group but remains unaffected in the EV and DNG-only groups 2. Based on this previous data, the effect size was estimated to be  $f = 0.25$  ( $f$  as defined by Cohen). With the significance level set at  $<0.05$  (the risk of a-error) and the desired power at 0.8 (risk of 1-b error), 16 participants were required in each of the three groups. We aimed to enroll 60 women to allow for possible discontinuation or loss during follow-up. We used the G\*Power software ([www.gpower.hhu.de](http://www.gpower.hhu.de)) for the sample size calculation.

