## Statistical Analysis

We will use IBM SPSS version 25 and 27 and Prism 9 (Graphpad) for Mac iOS for all statistical calculations. The significance level will be set at  $<0.05$ . Summarized data will be expressed as mean ( $\pm$ SD or 95%CI) or medians (ranges) as appropriate. The change from baseline will be described as mean (95%) or median (range) as applicable. Shapiro-Wilks test will test the normality of the data, and skewed variables will be log-transformed if needed. Comparisons of baseline demographic characteristics among the three groups will be performed using one-way analysis of variance (ANOVA). Repeated measures will be analyzed with one-way multiple measures ANOVA (analysis within-group) and two-way multiple measures ANOVA (analysis between groups) or the hierachal linear mixed model. Corrections for multiplicity (Bonferroni) will be applied. Parametric and nonparametric counterparts will be used to compare the within-group changes for secondary outcomes. The between-group changes from baseline will be analyzed by ANOVA or Kruskal-Wallis test with post hoc tests.

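### The between-group comparisons do not adjust for the baseline value, which gives up precision that would cost one degree of freedom

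*SAP*

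**What the plan says.** The Statistical Analysis section of the SAP gives three routes to a between-group comparison.

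- For changes: "The between-group changes from baseline will be analyzed by ANOVA or Kruskal-Wallis test with post hoc tests".
- For repeated measures, two further options joined by an 'or': "two-way multiple measures ANOVA (analysis between groups) or the hierachal linear mixed model".

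Baseline enters only by subtraction or as one of the repeated measurements. No ANCOVA and no covariate is named, and the mixed model is given without fixed effects. Baseline demographics are compared across groups, but that is descriptive. On scale, the section allows that "skewed variables will be log-transformed if needed".

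The Power Calculation section sets out the expected pattern for the Matsuda index: "we hypothesize that the Matsuda index decreases significantly in the EE group but remains unaffected in the EV and DNG-only groups". It requires 16 women in each of three groups and aims to enrol 60, that is 20 per group.

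**The concern.** A change score fixes the coefficient on baseline at 1. When baseline and follow-up are imperfectly correlated and have similar SDs, the best coefficient is smaller than 1, so subtracting the whole baseline value adds noise to the group comparison. ANCOVA estimates the coefficient from the data.

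The other two routes do not clearly avoid this. With two time points, the group-by-time test of a two-way repeated-measures ANOVA is the same test as ANOVA on change. A mixed model with group, time, their interaction and a random intercept also reproduces the change-score result. It recovers the precision only if baseline is a covariate or the baseline means are constrained equal across groups, and the SAP says neither.

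With 16 evaluable women per group and an effect expected in one group only, the between-group intervals will be wide. What is at stake is avoidable width in those intervals and avoidable loss of power, not validity.

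**Working it through.** **The plan's own figure.** The Power Calculation section uses "the effect size was estimated to be $f = 0.25", alpha 0.05 and power 0.8, and arrives at 16 per group. As a one-way ANOVA (noncentrality f² × N, df 2 and N − 3), f = 0.25 needs 53 per group, and power at 16 per group is 0.30. As a repeated-measures interaction (noncentrality f² × N × m/(1 − rho)), two measurements with rho 0.5 need 14 per group, and three measurements with rho 0.3 need 16. The SAP states neither the number of measurements nor rho, so 16 does not follow from the stated inputs alone. That does not show it to be wrong, and nothing below depends on it.

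**Inputs.**
- From the SAP: baseline SD s1 = 2.9, follow-up SD s2 = 2.8, and a fall of 7.3 − 5.6 = 1.7 in the EE group ("from 7.3 [ $\pm 2.9$ ] to 5.6 [ $\pm 2.8"); 16 or 20 per group; alpha 0.05.
- Assumed: rho from 0.3 to 0.9, the same SDs in all groups, raw scale, two time points, and mean changes of −1.7, 0 and 0, following the SAP's hypothesis.

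**Variances.**
- Change score: s1² + s2² − 2·rho·s1·s2 = 16.25 − 16.24·rho.
- ANCOVA: s2²(1 − rho²) = 7.84(1 − rho²).
- Difference between the two: (s1 − rho·s2)² = (2.9 − 2.8·rho)², which is positive for every rho. At rho 0.5 it is 1.5² = 2.25 = 8.13 − 5.88.

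**Pairwise standard error.** √(2·Var/n). For ANCOVA, Var is multiplied by 1 + 1/(3n − 5) to allow for estimating the slope; at n = 16 this is 1 + 1/43.

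**Power of the overall test.** By simulation, 60,000 trials per cell with the slope estimated; F on 2 and 3n − 3 df for change, 2 and 3n − 4 for ANCOVA. Each cell reads change score → ANCOVA.

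| rho (assumed) | Variance | Ratio | Pairwise SE, n = 16 | Power, n = 16 | Power, n = 20 |
|---|---|---|---|---|---|
| 0.3 | 11.38 → 7.13 | 0.63 | 1.19 → 0.96 | 28 → 41% | 34 → 51% |
| 0.5 | 8.13 → 5.88 | 0.72 | 1.01 → 0.87 | 37 → 49% | 46 → 59% |
| 0.7 | 4.88 → 4.00 | 0.82 | 0.78 → 0.72 | 58 → 66% | 69 → 77% |
| 0.8 | 3.26 → 2.82 | 0.87 | 0.64 → 0.60 | 76 → 81% | 86 → 90% |
| 0.9 | 1.63 → 1.49 | 0.91 | 0.45 → 0.44 | 97 → 98% | above 99% for both |

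**Cross-check.** The noncentral F has noncentrality n × 1.7² × (2/3)/Var. At rho 0.5 and n = 16, for change, this is 16 × 1.927/8.13 = 3.79, giving power 0.373 against 0.370 simulated. For ANCOVA the noncentral F runs up to about 1 point high because it ignores estimation of the slope.

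**Cost.** At 16 per group the residual df falls from 45 to 44, and the 5% critical F rises from 3.204 to 3.209.

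**Mixed model.** On one simulated two-time-point data set (16 per group, rho 0.7), the random-intercept model with group, time and interaction gave contrasts 0.926 and 1.744 with SE 0.894. ANOVA on change gave the same three numbers.

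**More visits.** With three equally correlated visits, equal SDs, and the mean of two follow-ups as the outcome, the ratio is [(1 + rho)/2 − rho²] / [1 + (1 + rho)/2 − 2·rho]. This is 0.56/1.05 = 0.53 at rho 0.3 and 0.14/0.15 = 0.93 at rho 0.9, still below 1.

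**The case against.** Analysis of change is a legitimate prespecified method, and the SAP does not contradict itself here. The strongest objections concern scope and size.

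1. **The mixed model is left open.** With a baseline covariate or constrained baseline means it would lose nothing, so on that route the SAP is silent rather than wrong. This stands: the loss there is conditional. Silence still lets the less precise version be fitted.
2. **The sentence on changes follows one about secondary outcomes and may mainly concern those, while the figures are for the Matsuda index.** This also stands. On that reading the Matsuda index falls under the repeated-measures sentence, which names no baseline covariate either.
3. **The gain depends on unstated inputs.** The correlation, the number of visits and any log-scale SDs are not in the SAP. If f = 0.25 is instead taken as a two-measurement interaction (also an assumption), noncentral F power at 16 per group goes from 72 to 90% at rho 0.3, 86 to 95% at 0.5 and 98 to 99% at 0.7. The gain is then negligible from rho 0.7. The size is uncertain, but it remains material at low to moderate correlation under either effect size.
4. **The powers are for the overall test, not for Bonferroni-corrected pairwise contrasts.** True. For those contrasts only the standard errors are given.
5. **The protocol might specify a covariate.** The SAP itself states the between-group method, and names no covariate in it, so this is not a topic left to another document.

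**Conclusion.** The concern holds. Followed as written, the change-score route and the repeated-measures route with two time points give less precise group contrasts than a baseline-adjusted analysis. The mixed-model route does so too unless baseline is handled in a way the SAP does not state.

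Under the listed assumptions, adjustment removes 37% of the variance at rho 0.3, 28% at 0.5, 18% at 0.7 and 9% at 0.9. At 16 per group the gain in overall power is about 13, 12, 8, 5 and 1 points at rho 0.3, 0.5, 0.7, 0.8 and 0.9.

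These are average gains; a single trial may see less. At very high correlation the benefit nearly vanishes. With equal SDs the variance ratio is (1 + rho)/2, and allowing for slope estimation it breaks even at 16 per group when (1 + rho)/2 = 43/44, that is rho of about 0.95. The change is worth making, but the plan is valid without it.

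**What to change.** In the Statistical Analysis section, state one between-group analysis for the Matsuda index and the other continuous outcomes. Either of these would do:

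- ANCOVA of the follow-up value with group and the baseline value of the same variable; or
- the mixed model already permitted, with baseline as a covariate or with baseline means constrained equal across groups, and its fixed effects written out.

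Use the log scale for both baseline and follow-up where the variable is skewed, as the section already allows. Report the adjusted EE–EV, EE–DNG and EV–DNG differences with 95% confidence intervals.

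The cost is SAP wording and one residual degree of freedom. No new data are needed, because change scores already require the baseline value, and the SPSS software named in the SAP fits both models.
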